This study evaluates the effect of a fractionated carbon dioxide laser on surgical scars of the face and neck over 12 months. Anyone with a surgical scar on the face and neck who has not had laser therapy may be eligible. The visits occur every three months for up to 12 months. Subjects will be randomly assigned to receive two high energy treatments or two low energy treatments. During the study visits, the scars will be photographed pre-treatment and the subject will complete a questionnaire to rate the scar. Three physicians will also evaluate the scar: one as a live assessment and the other two will evaluate the scars after each visit using photographs. Patients will receive their assigned treatment, obtain post-treatment instructions, and a diary to record redness, swelling, pain, itching, or other skin changes after treatment. Patients and raters will be blinded to which therapy level the patient receives until the 9-month visit (Visit #3) at which time patients will be unblinded and offered to have a third high energy treatment if in the high energy treatment group or to have two high energy treatments if in the low energy treatment group.

Study Timeline

The study will occur over 14 months. Our tentative timeline consists of recruitment and screening to occur in November 2016-September 2017. Study visits and data collection would occur between November 2016 and September 2017. Preliminary data analysis and publication of preliminary results would occur between August 2017 and March 2018. Final data analysis and publication would be between October 2018 and January 2019.

Introduction

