The primary objective is to assess the efficacy of fractionated carbon dioxide laser in improving surgical scars. Objective assessment of the scars will involve the Vectra microtopographic imaging system to measure changes in the length of the scar. The Patient and Observer Scar Assessment Scale (POSAS) is a validated survey that will be utilized for subjective assessments of the vascularity, pigmentation, thickness, pliability, surface area, relief, pain, and pruritus.

The secondary objective will be to evaluate the tolerability of the laser, by assessing the severity and duration of known side effects of laser therapy such as erythema, edema, burning sensation, post-inflammatory pigment changes, infection, scarring, xerosis, pruritus, bronzing, and any other adverse events that arise following treatment. Patients will be given a 30-diary after each treatment to document this information.

Selection and Withdrawal of Study Subjects

Study Population

The study population will consist of 50 adult patients 18 years of age or older with surgical scars located on the head and neck.

Minors are not included due to the Mohs patient population being adults only who have undergone surgical excisions of skin cancers on the head or neck. Although participants are not

required to be patients in the Mohs clinic, scars and healing may be significantly different in children, making the data less reliable and difficult to interpret.

Inclusion and Exclusion Criteria

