For the inclusion criteria, adult patients of all Fitzpatrick phototypes who have surgical scars of the head and neck will be screened for this study. There is no data to suggest that there is a difference in the appearance of older (more than 1 year old from the initial injury) and newer scars (at least 8 weeks after surgery) post-therapy. Most scars are fully mature at exactly 1 year from the date of the initial injury, so in the "older scar" cohort one may presume (in the absence of any confirmed findings in the medical literature) that any changes to these scars post-therapy will be an effect from the laser. The minimum age of the scar will be eight weeks from the initial surgery, as the scar has healed enough to determine if additional fine tuning may be helpful. In addition, standard practice is to allow a scar to heal for 8 weeks before laser treatment. Therefore subjects may be enrolled in the younger scar group if the scar is 8 weeks – 51 weeks from occurrence, and enrolled in the older scar group if the scar is 52 weeks or older from time of occurrence. We will aim to recruit 20 patients with old scars (10 of which will be in the high energy treatment group, and 10 of which will be in the low energy treatment group). In terms of statistical analysis, we will review whether there is a difference between the post-treatment measurements and appearance of older scars and newer scars. Patients must be able to understand the informed consent, willing to come to the office for treatments and capable of following post-treatment instructions.

In terms of exclusion criteria, patients who have had prior laser treatments to the face and neck, have a history of keloid formation, scars resulting from non-surgical etiologies (i.e. minor trauma), isotretinoin use in the last 6 months prior to study enrollment, and allergy to topical lidocaine will not be eligible for the study.

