A screening visit will occur whereby patients deemed appropriate for the study will have the segment of the scar with the most deformity defined for objective evaluation at each session. Baseline photographs of this area will be obtained and demographic data about the surgery that created the scar, associated wound healing complications, age of the scar, and the Fitzpatrick skin phototype will be collected. Randomization will occur at this visit and patients will receive their first treatment at this visit. Prior to treatment application, subjects will cleanse their face with a gentle cleanser, such as Cetaphil, provided in the office in order to remove all lotion, creams, make up, and sunscreen. An optional topical or local anesthetic medication will be offered to the subject and if desired by the subject will be applied to the treatment area approximately 20 minutes prior to the procedure. If the scar is deeper, an injection of numbing medicine (lidocaine with epinephrine) may be used as well. Once this time passes and the numbing medicine is working, the subject will be escorted to the procedure room. The treatment areas will be wiped clean of the numbing cream prior to the procedure. Just prior to the procedure, the subject's eyes will be covered with eye shields to protect their eyes. The treatment time may vary, but generally takes 10 minutes or less. During this time, subjects will hear the laser, which sounds like a bee buzzing, and will feel some warmth. Most patients report minimal discomfort during the procedure. There may be pinpoint bleeding, bruising, and crusting depending upon the area and extent of the treatment. After the treatment, patients will be provided with a 30-day diary to daily record treatment-related reactions: redness, swelling, pain, itching or color changes following treatment. If the subject has a history of recurrent fever blisters/cold sores on the lips or face, the subject will be offered a three day prescription for an antiviral medication that the subject can fill at the subject's pharmacy to prevent a recurrence since laser treatments may increase the chance of recurrent episodes. The subject would take one pill every twelve hours the day prior to treatment, on the treatment day, and the first day post-treatment. The subject or their insurance plan must cover the cost of the medication. This may delay the treatment to a later date within 30 days of the screening visit. If antibiotic/antiviral medications are needed, you and/or your insurance company will be responsible for covering this cost.

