 - A topical anesthetic medication will be applied to the treatment area approximately 20 minutes prior to the procedure. If the scar is deeper, an injection of numbing medicine may be used as well. Once this time passes and the numbing medicine is working, the subject will be escorted to the procedure room. The treatment areas will be wiped clean of the numbing cream prior to the procedure.
 - Just prior to the procedure, the subject's eyes will be covered with eye shields to protect their eyes.
 - The treatment time may vary, but generally takes 10 minutes or less. During this time, the subject will hear the laser, which sounds like a bee buzzing, and will feel some warmth. Most report minimal discomfort during the procedure. There may be pinpoint bleeding, bruising, and crusting depending upon the area and extent of the treatment. After the treatment, the subject will be provided with a diary to daily record treatment-related reactions: redness, swelling, pain, itching or color changes following treatment.
 - The subject will be given a paper diary to record possible reactions such as redness, swelling, pain, itching or color changes following treatment

- You will be given post-treatment instructions:
 - Thoroughly wash your hands prior to touching the treatment area.
 - Gently clean the treated area with a mild cleanser 3 times per day. Splash the face with tepid water and pat dry with a paper towel or a clean soft washcloth. The goal is to lightly remove the exfoliating skin and crusting that develops after the laser procedure. This is a GENTLE process with NO scrubbing. Avoid picking or scratching at the treatment site, as the skin is very friable and sensitive. Picking or scratching can lead to pigmentation changes or further scarring.
 - After each cleaning, apply a coat of Vaseline with a cotton tipped applicator (i.e. Q-tip)
 - As the skin heals, it is common to see little dots ("peppering") all over the treated skin. These will come off with the cleansing process.
 - You will continue the wound care for 7 10 days, at which time you should begin applying sunscreen instead of Vaseline.
 - You can shower the next day and wash hair, but avoid very hot water
 - On not expose the treated area to sun or wind for at least two weeks after treatment. If you go outside, use sunscreen with zinc (SPF 30+) and wear a hat. Protecting your skin and limiting sun exposure ensures the best results.

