unintended sign (including an abnormal laboratory finding), symptom or disease temporally associated with the use of the study device, whether or not related to the study device.

Reporting of Adverse Events

Only AEs that occur during or following study treatment with the drug will be reported in the AE section of the source documents. Events recorded prior to study treatment with the drug will be reported in the Medical History section of the source documents as appropriate. All AEs occurring during the course of the study will be individually recorded in the source documents. A condition that is present prior to administration of study drug and that worsens after administration of study drug should be reported as an AE. Information regarding the onset, duration, severity, action taken, outcome, and relationship to study drug will be recorded. New or worsening abnormal laboratory values and/or vital signs are to be recorded as AEs if they are considered to be of clinical significance by the PI or meet the criteria of an SAE (see below). Unless a diagnosis is available, signs and symptoms must be reported as individual AEs in the source documents; a diagnosis is preferred.

Adverse events (AEs) will be monitored throughout the study. Subjects will be instructed to inform the Principal Investigator (PI) and/or study staff of any AEs. At each visit, subjects will be asked about AEs in a non-specific manner using open-ended questions so as not to bias the response (e.g., Has the subject had any changes since the last visit?). Specific inquiry regarding reported AEs will be conducted when applicable. All adverse events will be documented and recorded in the source documents.

Any subject who has an AE (whether serious or non-serious) or clinically significant abnormal laboratory test value will be evaluated by the PI and will be treated and/or followed up until the symptoms or values return to normal or to clinically acceptable levels, as judged by the PI. A physician, either at clinical site, or at a nearby hospital emergency room, will administer treatment for any serious adverse events (SAEs), if necessary. When appropriate, medical tests and examinations will be performed to document resolution of event(s).

Intensity Grading of AEs

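### The side-effect diary has no pre-treatment entry and no rule linking it to the pre-treatment ratings, so symptoms already in the scar can be counted as laser reactions

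*Combined protocol and SAP*

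**What the plan says.** Study Objectives sets the secondary aim: "The secondary objective will be to evaluate the tolerability of the laser, by assessing the severity and duration of known side effects of laser therapy". The same paragraph names the diary, given after each treatment, as the place where this is documented. Study Procedures issues it once the laser has been used and describes it as follows: "patients will be provided with a 30-day diary to daily record treatment-related reactions: redness, swelling, pain, itching or color changes following treatment". The Visit Flowchart for Visit #1 is similar: "The subject will be given a paper diary to record possible reactions such as redness, swelling, pain, itching or color changes following treatment". The lists for Visits #2 and #4 repeat this. None mentions an entry made before the laser is used.

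The scar is recorded before treatment by other means. The opening summary says: "During the study visits, the scars will be photographed pre-treatment and the subject will complete a questionnaire to rate the scar". Baseline photographs are taken at screening, a physician evaluates the scar at Visit #1, and a pre-treatment questionnaire is listed at Visits #1, #2 and #4. The POSAS provides "subjective assessments of the vascularity, pigmentation, thickness, pliability, surface area, relief, pain, and pruritus".

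On eligibility, "subjects may be enrolled in the younger scar group if the scar is 8 weeks – 51 weeks from occurrence". On adverse events, "A condition that is present prior to administration of study drug and that worsens after administration of study drug should be reported as an AE". Data Analysis and Statistical Considerations describes tests on clinical improvement scores between visits and says nothing about diary data.

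**The concern.** Four of the five diary items (redness, pain, itching, colour change) are also properties of a healing scar, and the POSAS rates them as vascularity, pain, pruritus and pigmentation. A subject whose scar was already red or itchy has to decide unaided which part of today's redness or itch is due to the laser. The post-treatment instructions, which tell subjects to expect redness, may push that decision towards the laser.

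The adverse event rule turns on worsening, and daily entries show worsening only against a starting level. The second diary has a related difficulty. The Safety section allows erythema to last from days to months and treatments are 3 months apart, so residue from the first treatment may still be present at the second.

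At stake are the per-arm descriptions of severity and duration, and the ability to see a tolerability difference between energy levels. A day-0 level on the diary's own scale cannot be recovered once the laser has been used.

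**Working it through.** **No figure to reproduce.** The documents give no diary severity scale, reaction rate, summary of duration or power, and the sample of 50 has no stated derivation. The check is therefore a reading of the text plus illustrations on assumed inputs.

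**Text.**
- Diary: issued after treatment, kept daily for 30 days, no earlier entry (Study Procedures; Visits #1, #2 and #4).
- Pre-treatment record: photographs and a scar rating. The pre-treatment questionnaire is probably the patient POSAS, but this is not stated. Swelling has no counterpart among the listed POSAS items.
- Link between the two: none stated. No rule defines a reaction relative to the earlier rating or says when it has resolved.

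**Duration.** Let *d* be the laser's own duration in days (below 30) and *b* the share of subjects with the symptom beforehand. Suppose all of those subjects log it on all 30 days, which is the worst case. Then

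mean recorded duration = (1 − b) × d + b × 30.

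Redness, with d = 21 as an assumed reading of several weeks (post-treatment instructions, Visit #1):
- b = 0.3: 0.7 × 21 + 0.3 × 30 = 14.7 + 9.0 = 23.7 days; 23.7 / 21 = 1.13
- b = 0.7: 0.3 × 21 + 0.7 × 30 = 6.3 + 21.0 = 27.3 days; 27.3 / 21 = 1.30
- If d is 30 or more, the diary ends at day 30 either way and the ratio is 1.0.

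Itching, with d = 3 as an assumed reading of the few days or less in the same instructions:
- b = 0.1: 0.9 × 3 + 0.1 × 30 = 2.7 + 3.0 = 5.7 days; 5.7 / 3 = 1.9
- b = 0.3: 0.7 × 3 + 0.3 × 30 = 2.1 + 9.0 = 11.1 days; 11.1 / 3 = 3.7

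The values of *b* are assumptions; the documents give none. Short-lived reactions are the more sensitive to background.

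**Between arms.** Let *r* be the true reaction rate, and let *b* be equal in both arms and independent of the reaction. Then

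observed rate = b + (1 − b) × r, and observed difference = (1 − b) × (true difference).

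Assume r = 60% (high) and 30% (low), 25 per arm and two-sided alpha 0.05, using the normal approximation for two proportions with a pooled variance under the null:

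| b | High | Low | Difference | Power |
|---|---|---|---|---|
| 0 | 60% | 30% | 30 points | 57% |
| 10% | 64% | 37% | 27 points | 48% |
| 30% | 72% | 51% | 21 points | 33% |
| 50% | 80% | 65% | 15 points | 22% |

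For b = 30%: 0.30 + 0.70 × 0.60 = 0.72 and 0.30 + 0.70 × 0.30 = 0.51. An equal background raises both rates and shrinks the gap; it does not create one.

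**The case against.** The strongest reply is that a baseline exists. Photographs and scar ratings precede treatment, four of the five diary items have a POSAS counterpart, and events before treatment go to Medical History. A reader might infer that the trial has no pre-treatment record of these symptoms; that is wrong. What remains is the missing link, on a scale that may differ from the diary's, with swelling uncovered.

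Second, the diary asks for treatment-related reactions, and adverse events receive a separate relatedness judgement. A reader might infer that existing symptoms are bound to be recorded as reactions. The documents support only that they can be. This stands, and the point is worded accordingly.

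Third, the error runs both ways. The 30-day limit can understate erythema that lasts for months. A reader might take the 7 to 10 days given for exfoliation as the length of redness, and infer a large multiplier with many subjects at the 30-day ceiling. The same instructions say redness lasts several weeks, so the documents do not support that.

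Fourth, the plan describes no high versus low test of diary data, so the power figures illustrate a comparison it does not specify. Nor does it plan a scar-age analysis of the diary: the older versus newer comparison concerns post-treatment measurements and appearance. Any inference that this comparison is confounded through the diary therefore fails.

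Finally, resetting the reference at each treatment would turn persistent laser erythema into the new normal and hide it. That is correct, and the fix allows for it.

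**Conclusion.** The point holds in limited form. The diary for the secondary objective has no pre-treatment entry and no rule connecting it to the ratings that precede treatment. Symptoms already in the scar, most plausibly in newer scars, can therefore be logged as laser reactions. Per-arm severity and duration can be overstated and, with a similar background in both arms, a difference between energy levels would be diluted.

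The size is unknown, because the documents give neither the share of scars with symptoms beforehand nor the diary's scale. For redness it is probably modest: at most 1.13 to 1.30 times under the 21-day assumption, and none if laser redness lasts 30 days or more. For itching the ratio could be larger, 1.9 to 3.7, but only if 10% to 30% of scars itch beforehand and those subjects log it every day. The change should be made because it costs little and the missing entry cannot be reconstructed later.

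**What to change.** Add a day-0 line to each diary, completed just before treatment and ideally before the area is cleansed or numbed (the Safety section lists redness, itching and swelling as effects of the anaesthetic). It should rate the same five items on the same scale as the daily entries. If the first treatment is deferred within the permitted 30 days, day 0 is the treatment day, not the screening day.

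Add to the protocol and its analysis section:
- A reaction is any level worse than the day-0 entry for that treatment.
- Its duration is the number of days until return to that entry, censored at day 30 if unresolved.
- For the second and later treatments, the level is also reported against the day-0 entry before the first treatment, so that lasting redness or pigment change counts as persistence.

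The cost is one extra diary line per treatment, where 5 minutes a day is already allotted, and a short paragraph of text. Reported reaction rates and durations will be lower than raw diary counts, and the report should say why. No treatment or visit changes.
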